3.4 Randomization and Stratification Factors

Eligible subjects will be enrolled in the study and sequentially assigned an identification number. Subjects will be randomized in a 1:1 ratio to UX007/Placebo or Placebo/UX007 treatment sequence via an Interactive Web Randomization System (IWRS) based on a randomization schedule developed by an independent third-party vendor to maintain blinding. The randomization procedure will be performed without stratification.

3.5 Blinding

The Titration and Maintenance Periods (Weeks 0-22) will be conducted as a randomized, double-blind, placebo-controlled, crossover study. Double-blind conditions will be established during this period so that neither the sponsor, subject, or site personnel involved in study conduct will know the identity of a subject's treatment. After all subjects have completed the double-blind period, unblinding of the study will occur post the double-blind portion of the study database is locked. All subjects who complete the double-blind portion of the study will be eligible to receive open-label UX007 during the Extension Period to assess long-term safety and duration of effect.

The Investigator and site personnel will remain blinded to the randomization code during the double-blind portion of the study. Treatment assignment for an individual subject should be unblinded by the Investigator only in an emergency e.g., event concerning subject safety, and only if knowledge of the treatment assignment is urgently needed for the clinical management or welfare of the subject. The Investigator should contact the medical monitor before unblinding, when possible, but priority should be given to the safety of the subject.

If a subject's treatment assignment is unblinded prior to completion of the double-blind portion of the study, the subject may be discontinued from the study and may not be eligible to participate in the open-label Extension Period. Detailed blinding procedures are specified in the study protocol.

3.6 Sample Size Considerations

The primary efficacy parameter is number of disabling paroxysmal movement disorder events observed during the Maintenance Period of Treatment Periods I and II. Based on the targeted patient population and eligibility criteria, it is estimated that during a 6 week duration, the subjects receiving placebo will have a mean frequency of 8 disabling paroxysmal movement disorders per 4 weeks, while subjects receiving UX007 will have a mean frequency of 4 disabling paroxysmal movement disorders per 4 weeks, and a standard deviation of the difference of 7.4. A total sample size of 40 subjects (20 subjects in each treatment sequence) will have at least 85% power to detect such difference between UX007 and placebo groups at the two-sided 5% significance level. This sample size assumption incorporates a projected discontinuation rate of 15%.

3.7 Interim Analysis

There is no interim analysis planned for this study.

3.8 Primary Analysis

The primary analysis will occur when all subjects have completed the DB Treatment Period, or withdrawn from the study during the DB Treatment Period, whichever comes earlier.

3.9 Final Analysis

The final analysis will occur when all subjects have completed the OLE Period, or withdrawn from the study, whichever comes earlier.

Additional analyses may be performed after primary analysis during the course of the study at the discretion of the Sponsor.

3.10 Data Monitoring Committee (DMC)

An independent DMC with that includes members with expertise in movement disorders will act in an advisory capacity to monitor subject safety on a routine basis throughout the trial. The DMC may also provide advice to Ultragenyx in any determination of whether study enrollment should be paused or if the study should be halted. The detailed roles and responsibilities of the DMC are specified in the DMC Charter.

4 STUDY ENDPOINTS AND COVARIATES

All data are collected according to the schedule of assessments (Section 10.2 Appendix B and Section 10.3 Appendix C).

4.1 Primary Efficacy Endpoints

The primary efficacy endpoint is frequency of disabling paroxysmal movement disorder events during the maintenance treatment period, as recorded by the subject/caregiver in an event-based daily Glut1 DS symptom diary.

4.2 Secondary Efficacy Endpoints

- Total duration of disabling paroxysmal movement disorder events during maintenance phase, as recorded by the subject/caregiver in an event-based daily Glut1 DS symptom diary
- Change from period baseline to treatment week 10 in 12 Minute Walk Test (12MWT) distance
- Patient/caregiver Clinical Global Impression – Improvement (CGI-I) score at treatment week 10
- Change from period baseline to treatment week 10 in Patient Reported Outcomes Measurement Information System (PROMIS) scores (domain scores)
- Change from period baseline to treatment week 10 in the following Cambridge Neuropsychological Test Automated Battery (CANTAB) scores (assessed at select sites)
 - Spatial Span (SSP):
 - Span Length (SSPSLF)
 - Spatial Working Memory (SWM):
 - Between Errors (SWMBE48)
 - Strategy (SWMS68)
 - Paired Associates Learning (PAL):
 - Total Errors (Adjusted) (PALTEA)
 - First Trial Memory Score (PALFTMS)

4.3 Exploratory Efficacy Endpoints

- Change from period baseline in performance score and in satisfaction score as assessed by Canadian Occupational Performance Measure (COPM) at treatment week 10
- Physician CGI-I score at treatment week 10
- Change from period baseline in physician Clinical Global Impression-Severity (CGI-S) score at treatment week 10
- Change from study baseline to treatment week 10 in mean daytime activity, mean nighttime activity, and percent time in moderate or higher intensity activity as measured by a wrist-worn actigraphy device at select study sites where feasible
- Frequency of disabling paroxysmal movement disorder events over time throughout the three-year OLE period.
- Total duration of disabling paroxysmal movement disorder events over time throughout the three-year OLE period
- PK data for UX007 metabolites
- Efficacy Endpoints during the three-year OLE period: 12MWT, Patient/caregiver CGI-I, CANTAB, Physician CGI-I, Physician CGI-S, performance score and satisfaction score as assessed by COPM, PROMIS scores (domain scores)

4.4 Safety Endpoints

- Adverse events (AEs), including the subject incidence of AEs, treatment related AEs, serious adverse events (SAEs), AEs leading to discontinuation and fatal AEs
- Vital signs
- Clinical laboratory test results
- Electrocardiogram (ECG)
- Suicidal ideation and behavior assessment as measured by the Columbia Suicide Severity Rating Scale (C-SSRS)

4.5 Covariates

For the analysis of covariate (ANCOVA) analysis, baseline (study baseline or period baseline) of the response variable will be included as the covariates, whenever appropriate. Sequence and period will also be included as the covariates, when analyzing the DB treatment data.

4.6 Subgroups

Using information from the Ketogenic Diet CRF form, the following subgroups are identified to examine any potential treatment effect.

1. Subjects who have never tried a prescribed diet plan to manage Glut1 symptoms.
2. Subjects who have tried a prescribed diet plan to manage Glut1 symptom and the most recent prescribed diet (KD/Modified Atkins Diet/other) was discontinued due to lack of efficacy.
3. Subjects who have tried a prescribed diet plan to manage Glut1 symptom and the most recent prescribed diet (KD/Modified Atkins Diet/other) was discontinued for a reason or reasons other than lack of efficacy.

5 DEFINITIONS

5.1 Study Day

- If the assessment date is on or after the first dose date of investigational product:
- Study day = (assessment date – first dose date of investigational product + 1)
- If the assessment date is prior to the first dose date of investigational product:
- Study day = assessment date – first dose date of investigational product

5.2 Study Week/Treatment Week

Study weeks are the time points recorded on CRF.

For the DB treatment period, treatment weeks are defined as:

- For subjects randomized to UX007/Placebo group
 - UX007 treatment week=study week
 - Placebo treatment week=study week-12
- For subjects randomized to Placebo/UX007 group
 - Placebo treatment week=study week
 - UX007 treatment week=study week-12

5.3 Duration of Exposure

- Duration of exposure to Investigational Product (IP) (Placebo or UX007), in days, is defined as:
 - During the DB Treatment Period: defined as last dose date of IP in the corresponding treatment period of the DB Period – first dose date of IP in the corresponding treatment period of the DB Period + 1 day
- Duration of exposure to UX007, in days, is defined as:
 - During the OLE Period is defined as last dose date of UX007 in OLE Period – first dose date of UX007 in OLE Period + 1 day
 - During the whole study is defined as the sum of the duration of exposure to UX007 in days during the DB Treatment Period and the duration of exposure to UX007 in days during the OLE Period

5.4 Age

Age will be derived based on the informed consent date as $\text{Age} = (\text{Inform Consent Date} - \text{Birth Date} + 1) / 365.25$. Age will be rounded down and keep 1 decimal place. When date of birth is missing, then age recorded on case report form (CRF) at time of informed consent will be used.

5.5 Baseline

- Movement Disorder:

Study baseline for movement disorder frequency as recorded by the subject/caregiver in diary will be normalized to a 4-week rate as

$$\frac{\text{total number of movement disorder events during the 6 weeks run-in period} \times 28}{\text{number of days with diary data during the 6 weeks run-in period}}$$

Study baseline for total duration of movement disorder in hours will be normalized to a 4-week rate as

$$\frac{\text{total duration of movement disorders in hours during the 6 weeks run-in period} \times 28}{\text{number of days with diary data during the 6 weeks run-in period}}$$

- For other efficacy endpoints, study baseline is defined as the last non-missing assessment prior to or on the date of the first dose of investigational product
- For safety endpoints, study baseline is defined as the last non-missing assessment prior to or on the date of the first dose of investigational product

Period baseline is defined as the last non-missing assessment prior to or on the date of the first dose of investigational product for each DB treatment period. A value from the first treatment period will not be considered as the period baseline for the second treatment period.

5.6 Movement Disorder Frequency and Total Duration

For analyses, movement disorder frequency and total duration in hours will be normalized to a 4-week rate at each of the specified period:

$$\frac{\text{total number of movement disorders during the specified period} \times 28}{\text{number of days with diary data during the specified period}}$$

$$\frac{\text{total duration of movement disorders during the specified period} \times 28}{\text{number of days with diary data during the specified period}}$$

Mean duration in hours at each of the specified period is defined as:

$$\frac{\text{total duration of movement disorders during the specified period}}{\text{total number of movement disorders during the specified period}}$$

The percentage of movement disorder free days is defined as

$$\frac{\text{total number days with of zero movement disorder}}{\text{number of days with diary during the specified period}} * 100\%$$

5.7 Percent Predicted Six Minute Walk Test (6MWT) Distance

To calculate the percent predicted 6MWT value, the following formulas will be applied (Geiger et al. 2007) for subjects aged <20 years old at randomization:

$$\text{For Males: } X_i = \frac{X_{0i}}{196.72 + (39.81 * \text{Age}) - (1.36 * \text{Age}^2) + (132.28 * \text{Height})} * 100$$

$$\text{For Females: } X_i = \frac{X_{0i}}{188.61 + (51.50 * \text{Age}) - (1.86 * \text{Age}^2) + (86.10 * \text{Height})} * 100$$

Where:

X_i = The percent predicted 6MWT result at time i for subject X

X_{0i} = The 6MWT (m) result at time i for subject X

To calculate the percent predicted 6MWT value, the following formulas will be applied (Gibbons et al. 2001) for subjects aged ≥ 20 years old at randomization:

$$X_i = \frac{X_{0i}}{868.8 - (2.99 * \text{Age}) - (74.7 * \text{Women})} * 100$$

Where:

X_i = The percent predicted 6MWT result at time i for subject X

X_{0i} = The 6MWT (m) result at time i for subject X

$Women$ = an indicator variable: equal to 1 if the subject is female and 0 if male

The percent predicted 6MWT formulas will use the subject's height (m) and age at the randomization visit throughout the study duration.

5.8 PROMIS Scores

The PROMIS questionnaires have been developed from the Adult and Pediatric PROMIS Item Banks (Broderick et al. 2013) (NIH 2015). Self- and proxy-report versions are available and use is based on participant age and cognitive ability. The responses collected from PROMIS questionnaires will be uploaded to the web-based application, HealthMeasures Scoring Service, to obtain the final T-scores for each domain listed below (<http://www.healthmeasures.net/score-and-interpret/calculate-scores>).

For adults, T-scores will be derived for the following domains:

- physical function
- fatigue
- sleep disturbance
- pain interference
- cognitive function
- ability to participate in social roles and activities
- anxiety

For pediatric subjects (under the age of 18), T-scores will be derived for the following domains,

- mobility
- upper extremity
- fatigue
- pain interference
- peer relationships

5.9 Physician and Patient/Caregiver CGI Scales

Physician CGI-S score and patient/caregiver CGI-S score use a 4-point Likert scale (1 = Normal to 4 = Severe) to rate disease severity.

Physician CGI-I score and patient/caregiver CGI-I score use a 7-point Likert scale (1 = Very much better to 7 = Very much worse) to record the degree of change in clinical status.

5.10 COPM

Up to five most important occupational performance problems as reported by the subject/parent/caregiver at the Study Week 0 visit will be scored using a scale of 1-10 (1 = poor performance and low satisfaction to 10 = very good performance and high satisfaction) to provide a Performance score and a Satisfaction score for each of the occupational performance problems.

The performance or satisfaction score can be derived as:

$$\frac{\text{Sum of performance or satisfaction scores}}{\text{Number of problems that were actually answered}}$$

5.11 Activity measurements by Actigraphy Device

A wrist-worn activity monitor (actigraphy device) will assess the impact of Glut1 DS on activity at select study sites, where feasible. The endpoints will be measured during the last 10 days of the Run-in Period, the last 10 days of Treatment Period 1, and the last 10 days of Treatment Period 2. The endpoints are defined as following:

Mean daytime activity: Average activity count during worn epochs between the hours of 10 a.m. and 8 p.m in the last 10 days of the specified period. If there are no worn epochs, the value will be -1

Mean nighttime activity: Average activity count during worn epochs between the hours of 12 a.m. and 5 a.m in the last 10 days of the specified period. If there are no worn epochs, the value will be -1

Percent time in moderate or higher intensity activity: The ratio of total minutes in moderate to vigorous physical activity to total wear minutes. This will be -1 if there no wear minutes.

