7.2 Handling of Missing and Incomplete Data

Missing clinical outcome data can occur for multiple reasons, including missed subject visits and scales or measures with missing item scores. Missing and incomplete data will be identified for investigation and possible resolution by Data Management prior to the study database lock or snapshot.

Unless specified otherwise, only the observed data will be presented. When a change from baseline is assessed, only patients with a baseline and at least one post-baseline measurement will be included in the analysis.

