8.8.3 Analyses of Exploratory Efficacy Endpoints

An ANCOVA model with period baseline as a covariate, treatment sequence, treatment group, period as fixed effects, and a random effect for subject within the sequence, will be used to analyze change from period baseline to treatment week 10 in performance score and change from period baseline to treatment week 10 in satisfaction score as assessed by COPM.

An ANCOVA model with study baseline as a covariate, treatment sequence, treatment group, period as fixed effects, and a random effect for subject within the sequence, will be used to analyze the following other efficacy endpoints:

- Physician CGI-I score at treatment week 10, the Physician CGI-S study baseline will be used as an explanatory variable
- Physician CGI-S score at treatment week 10, the Physician CGI-S period baseline will be used as an explanatory variable
- Change from study baseline to treatment week 10 in mean daytime activity, mean nighttime activity, and percent time in moderate or higher intensity activity as measured by a wrist-worn actigraphy device at select study sites where feasible

Frequency, mean duration and total duration of disabling paroxysmal movement disorder events over time throughout the three-year OLE period will be summarized. Change from

study baseline in percentage of movement disorder free days during the three-year OLE period will also be summarized.

Efficacy Endpoints during the three-year OLE period including 12MWT, Patient/caregiver CGI-I, CANTAB, Physician CGI-I, Physician CGI-S, performance score and satisfaction score as assessed by COPM, PROMIS scores (domain scores) will be summarized and study baseline will be used.

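### SAP 5.11 sets the actigraphy endpoints to -1 when the device was not worn, and no rule removes that value before the ANCOVA in SAP 8.8.3 (minor: exploratory endpoints)

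*SAP*

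**What the plan says.** SAP 5.11 defines three wrist-actigraphy endpoints, measured over the last 10 days of the Run-in and of each treatment period. For mean daytime and mean nighttime activity the rule is "If there are no worn epochs, the value will be -1". For percent time in moderate or higher intensity activity it is "This will be -1 if there no wear minutes".

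SAP 8.8.3 specifies the model, whose random subject effect is nested in treatment sequence: "An ANCOVA model with study baseline as a covariate, treatment sequence, treatment group, period as fixed effects, and a random effect for subject within". Among the outcomes it lists is "Change from study baseline to treatment week 10 in mean daytime activity, mean nighttime activity, and percent time in moderate or higher intensity activity". Appendix A repeats this as ANCOVA on the Full Analysis Set, with No in the imputation column.

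The general rule in SAP 7.2 is "Unless specified otherwise, only the observed data will be presented". Protocol 7.6.3.1 likewise leaves missing data as missing, again with an exception for anything stated elsewhere. Neither document calls -1 a flag, sets it to missing, or excludes it before the change score or the model.

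The endpoints are exploratory and collected only at select sites where feasible (protocol 6.1.3, SAP 4.3). They are not in the sequential testing order of SAP 8.8.2.

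**The concern.** A no-wear code has been written into the endpoint definition as a number, and the next instruction is to model that endpoint. A program that follows the SAP literally treats a period with no data as an observed, very low activity level. SAP 8.8.3 also lacks the normality check and rank-test fallback that SAP 8.8.1 and 8.8.2 apply to other endpoints, so nothing downstream would blunt the outlying value. At stake are the estimate and standard error of a planned, though exploratory, between-treatment comparison.

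**Working it through.** The plan states no actigraphy figure to reproduce. The check is a reading of the text, followed by illustrative arithmetic on assumed inputs.

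**1. Can -1 be a measurement?** The daytime endpoint is "Average activity count during worn epochs between the hours of 10 a.m. and 8 p.m in the last 10 days of the specified period", and the nighttime endpoint has the same form, so both are at least 0. The intensity endpoint is "The ratio of total minutes in moderate to vigorous physical activity to total wear minutes", so it lies between 0 and 1. The value -1 is impossible for all three.

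**2. Change scores if -1 is kept** (b = study baseline, y = treatment-period value)
- No wear in a treatment period: -1 - b. For b = 100 counts this is -101; for a ratio of 0.10 it is -1.10.
- No wear at Run-in: y + 1, with a covariate of -1.
- No wear at both: 0, which reads as no change.

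**3. Shift in one treatment's mean from one post-baseline non-wearer:** -(m + 1)/n, with assumed mean m and n wearers.

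| Endpoint | m | n = 20 | n = 10 |
|---|---|---|---|
| Count | 50 | -51/20 = -2.55 (5.1% of m) | -51/10 = -5.1 (10.2%) |
| Count | 100 | -101/20 = -5.05 (5.1%) | -101/10 = -10.1 (10.1%) |
| Count | 200 | -201/20 = -10.05 (5.0%) | -201/10 = -20.1 (10.1%) |
| Intensity, as a ratio | 0.10 | -1.10/20 = -0.055 (55%) | -1.10/10 = -0.11 (110%) |
| Intensity, on a 0-100 scale | 10 | -11/20 = -0.55 (5.5%) | -11/10 = -1.1 (11%) |

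**4. Direction.** Take the ratio endpoint with n = 16, placebo mean 0.10 and true gain 0.02.
- Non-wearer in the UX007 period: 0.02 - 1.12/16 = -0.050.
- Non-wearer in the placebo period: 0.02 + 1.10/16 = +0.089.
- Average of the two: about +0.019, close to the truth.

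**5. Variance.** If one within-subject difference is displaced by D and the other n - 1 vary little, the sample variance of the differences is about D²/n. The standard error is then about D/n, the same size as the shift. For D = 1.12 and n = 15, 1.12/15 = 0.075. A simulation with within-subject SD 0.02 gave a standard error of 0.075, against 0.007 without the coded value.

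**6. Crossover simulation for counts.** Assumed inputs: 20 wearers, mean 100, SD 30, within-subject correlation 0.7, 2,000 runs, within-subject differences adjusted for sequence and period. Under missing, affected subjects are dropped from the paired comparison.

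| True effect | Non-wearers, UX007 / placebo | Estimate, missing | Rejection, missing | Estimate, -1 kept | Rejection, -1 kept |
|---|---|---|---|---|---|
| 0 | 1 / 1 | 0.2 | 5.0% | -0.2 | 0.3% |
| 0 | 3 / 0 | 0.2 | 5.1% | -15.1 | 17.6% |
| 20 | 1 / 1 | 20.0 | 93.0% | 18.9 | 41.9% |
| 20 | 2 / 0 | 20.1 | 92.8% | 7.9 | 2.5% |

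The arithmetic agrees: 20 - (2/20) × 121 = 7.9, and -(3/20) × 101 = -15.15.

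**7. No wear at Run-in.** One study baseline serves both periods. For a subject with both periods, (y1 - b) - (y2 - b) = y1 - y2 whatever b is. The SAP model was fitted to five simulated complete data sets of 16 subjects, with and without one baseline set to -1. The treatment estimate was the same to five decimals in all five. The standard error agreed in four and was 0.0069 versus 0.0073 in the fifth.

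**The case against.** The best defence is that -1 is plainly a device flag. With no worn epochs nothing was observed, so SAP 7.2, protocol 7.6.3.1 and the No in Appendix A would lead a sensible programmer to drop it. That may well be what would happen. However, both general rules yield to a specific one, and SAP 5.11 is specific. The Appendix A entry does not settle it, because a record already holding -1 needs no imputation. The outcome is left to the programmer.

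Other parts of the defence stand:
- The mean-activity codes apply only when there is no wear at all in the relevant hours across the 10-day window; partial wear is averaged.
- The large relative shift belongs to the intensity endpoint taken as a ratio. That endpoint is named as a percentage but defined as a ratio; on a 0-100 scale the shift is about the size of that for counts.
- Reversal of the sign needs the non-wearer to fall in the UX007 period.

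A reader might also infer that non-wear differs by treatment or tolerability, so that the error is systematically directional. Nothing in the documents supports this; the one-sided rows in the simulation show what would follow if it happened. A reader might likewise infer that a Run-in -1 corrupts the treatment estimate. Step 7 shows that it largely cancels; what it distorts is the covariate and the summaries of change.

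**Conclusion.** Wrong as written, minor in severity. Following SAP 5.11 and 8.8.3 literally puts an impossible value into the model for any treatment period without wear. One such subject among 10 to 20 moves a treatment mean by about 5% to 10% for the count endpoints, and by -0.055 to -0.11 for a ratio of 0.10. The sign of the effect on the treatment difference depends on the period affected, and the variance is inflated in either case. These sizes rest entirely on assumed means, SDs, wearer numbers and non-wear counts, because the documents give none.

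Two stronger inferences should not be drawn. The text does not show that the data were, or will be, analysed with -1 kept; it shows that the plan does not prevent it. Nor does the point reach the trial's main conclusions: the endpoints are exploratory, limited to select sites and outside the testing hierarchy, so the primary and key secondary results are untouched.

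**What to change.** Add to SAP 5.11: a value of -1 denotes no wear; it is set to missing, at study baseline and in both treatment periods, before any summary, change score or model. Report the number of no-wear records by treatment and period, so that any imbalance is visible.

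This takes one or two sentences, with no new data and no burden on subjects. There is a small downside. Under SAP 7.2 a change analysis needs a baseline, so a subject with no Run-in wear drops out of it even when both treatment periods are valid.
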